#### 7.4 HANDLING OF MISSING DATA

Missing data will not be imputed in general. All patients will be followed to collect necessary efficacy and safety information, even if patients discontinue study medication prematurely.

#### 7.5 RANDOMISATION

Randomisation is in general not applicable to this study. Only patients assigned to OLF will be randomized based on 1:1 ratio to receive flavoured or unflavoured solvent for reconstitution.

#### 7.6 DETERMINATION OF SAMPLE SIZE

The design of this study (including the definition of endpoints and sample size) has been agreed with the European Medicines Agency's Paediatric Committee. A minimum of 100 patients will be entered in this trial, including patients rolling over from study 1160.106, who require secondary VTE prevention and new patients who should have completed treatment for an acute VTE episode. The Data Monitoring Committee (DMC) or Sponsor may decide to keep recruitment open after 100 patients have been recruited, in case additional safety data needs to be generated.

Under the assumption of 5% of event rate for the composite of recurrent VTE, major bleeds and mortality related to thromboembolic event at 12 months, 100 patients will provide more than 99% of probability observing at least 1 event, it will provide higher than 63% of probability if the event rate is 1%. The expected 95% Wilson confidence interval for event rates under the assumption of 100 patients are provided in Table 7.6: 1.

Table 7.6:1 Expected 95% Wilson confidence interval based on 100 available patients

Observed rate (%)	95% Wilson CI
1	(0.18 – 5.45)
2	(0.55 – 7.00)
3	(1.03 – 8.45)
4	(1.57 – 9.89)
5	(2.15 – 11.2)
10	(5.52 – 17.4)
20	(13.3 – 28.9)

The sample size is considered adequate to capture any safety signal for the primary safety endpoints defined in the study.

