### 3. DESCRIPTION OF DESIGN AND TRIAL POPULATION

#### 3.1 OVERALL TRIAL DESIGN AND PLAN

This is a multi-centre, multinational, open-label, single arm prospective cohort study of dabigatran etexilate to evaluate safety in the secondary prevention of venous thromboembolism in children from 0 to less than 18 years. This study is planned to be conducted in approximately 100 sites located worldwide.

After a signed consent form (and assent, if applicable) has been obtained and if all eligibility criteria are met, patients will initiate or continue treatment with dabigatran etexilate (Visit 2). Detailed guidance on how to switch from standard VTE treatment to dabigatran etexilate is provided in [Section 4.1.4](#).

Patients will be treated with dabigatran etexilate until the clinical risk factor requiring secondary VTE prevention has resolved, or up to a maximum of 12 months. The clinical risk factor must be specified at screening and evaluated at every visit. At the end of the study all patients need to discontinue dabigatran etexilate, or switch to standard of care, if there is continued need for anticoagulant treatment (see [Appendix 10.3](#)).

Please refer to [Section 4.1.3](#) for information on dose selection.

Study visits and procedures will be performed as outlined in the [Flow Chart](#). Collection and processing of PD samples is described in [Section 5.7.2](#).

All patients who have taken dabigatran etexilate will have a follow-up period of 28 days after termination of trial medication (Visit 11). Subject participation is concluded when the Follow-up Visit is completed.

Patients who stop study treatment earlier than 12 months (risk factor resolved or early treatment discontinuation) will be asked to perform an eEOT Visit and will be followed up according to the remaining visit schedule until the end of the study. Prior to entering the trial, patients and their parents / legal guardians will be made aware of this requirement.

The end of the trial is defined as “last subject out”, i.e. last visit completed by the last subject.

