**Proprietary confidential information.**

© 2019 Boehringer Ingelheim International GmbH or one or more of its affiliated companies. All rights reserved.

This document may not - in full or in part - be passed on, reproduced, published or otherwise used without prior written permission.

- If the patient develops renal dysfunction anytime during the course of the study (eGFR < 50 mL/min/1.73m^2 using the Schwartz formula, confirmed by one retesting within the next 14 calendar days). If a patient develops eGFR < 50 mL/min/1.73m^2 using the Schwartz formula for a second time during the course of the study, treatment with dabigatran etexilate must be stopped without further retesting
- If the patient does not require treatment with anticoagulants any longer due to resolution of the underlying clinical risk factor prior to 12 months of planned anticoagulation treatment. In such cases, an early EOT Visit is to be performed and the patient should still be followed up according to the remaining visit schedule until the end of the study.

In order to protect patient safety, measurements of dabigatran trough plasma levels will be performed in a central laboratory

If a patient has a dabigatran plasma level of < 50 ng/mL or ≥ 250 ng/mL confirmed despite a dose adjustment, they will be discontinued from trial treatment and must be switched to an appropriate alternative therapy at investigator's discretion.

Dabigatran is predominantly excreted by the kidney; special attention should be given to the kidney function of these patients when needed. As stated above, any patient with confirmed eGFR < 50 mL/min/1.73m^2 using the Schwartz formula at any time during the treatment period will be discontinued from trial treatment. Any suspected worsening of renal function during the study should be investigated by eGFR evaluation.

Patients who discontinue study drug or withdraw from the trial after being entered (Visit 2) will be considered as “early discontinuations” and will not be replaced. The reason for premature discontinuation must be recorded in the eCRF. The data will be included in the trial database and will be reported.

Patients who discontinue study drug prior to 12 months of planned treatment due to resolution of the underlying clinical risk factor will not be considered as “early discontinuations”.

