### 6.2.3 End of trial and follow-up period

Follow-up Visit should be planned for 28 days after last drug intake. For the assessments and procedures to be done during the Follow-up Visit refer to the [Flow Chart](#).

All patients who prematurely discontinue treatment will be invited to perform an eEOT Visit. Subsequently they will be followed up according to the remaining visit schedule until the end of the study. At these visits collection of AEs, outcome events (e.g. occurrence of PTS, VTE, bleeding events, etc.) and use of concomitant medication will be made.

Patients that are not actively taking study drug and their parent/legal guardian may be less motivated to adhere to the study visit schedule. Investigator and site staff should work to detect early signs of losing interest and readily present such patients (not actively taking study drug) and their parent/legal guardian with the following opportunities to encourage continued participation:

- continue to attend regularly scheduled study visits until the trial ends
- conduct only the final visit in person. All other visits would be done over the phone.
- conduct all remaining study visits over the phone
- discontinue participation in remaining trial activities but permit collection of vital status and outcome events at the end of the trial.
- discontinue participation in remaining trial activities but permit collection of vital status at the end of the trial.

The patient / parent / legal guardian will be asked to choose the most rigorous follow-up they are willing to comply with.

For patients who completely withdraw consent no more data on their medical information will be requested.

The site must make periodic documented attempts (approximately every three months) to locate patients who are lost to follow up (LTFU).

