#### 7.3.1 Primary analyses

The primary analyses will be based on the primary safety endpoints. The recurrence of VTE, major bleeding events, minor (including clinically relevant non-major (CRNM)) bleeding events, overall mortality and mortality related to thromboembolic events will be analysed as time-to-event and will be summarized by Kaplan-Meier estimates. The rate of occurrence of events at 6 and 12 months will also be provided by K-M estimation. Patients who do not have any of the events or drop out early will be considered as censored for this analysis. Additionally, descriptive rate with number of patients with event divided by total treated patients will also be provided. Early drop out and lost-to-follow-up will be considered as non-event. The components of the composite event will be summarized as below:

- Recurrence of venous thromboembolism will be summarized by Kaplan-Meier estimate of time to first recurrence of VTE. The rate of recurrence at 6 and 12 months will also be provided by K-M estimation. Patients, who do not experience recurrent VTE by the time of analyses, drop out from the study, or die from non-VTE related cause will be considered as censored. The descriptive rate of number of patients with event divided by total treated patients will also be provided. Early drop out and lost-to-follow-up will be considered as non-event when calculating the descriptive rate.
- Major bleeding and minor (including clinically relevant non-major (CRNM)) bleeding will be analysed by K-M estimate of time to first occurrence as competing events. The K-M rate estimate at 6 and 12 month will be provided. The descriptive rate will also be calculated by dividing number of patients with major / minor bleeding by the number of total treated patients. Early drop out, lost-to-follow-up and non-bleeding related death will be considered as non-event and censored.

Proprietary confidential information.

© 2019 Boehringer Ingelheim International GmbH or one or more of its affiliated companies. All rights reserved.

This document may not - in full or in part - be passed on, reproduced, published or otherwise used without prior written permission.

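### At the minimum of 100 patients entered, the detection probabilities in Section 7.6 are upper bounds, because they need 100 patients each observed for 12 months; one limit in Table 7.6:1 is also wrong

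*Protocol*

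**What the plan says.** Section 7.6 of the protocol sets the size as "A minimum of 100 patients will be entered in this trial", and adds that the Data Monitoring Committee or the sponsor "may decide to keep recruitment open after 100 patients have been recruited". It assumes a 5% rate at 12 months for the composite of recurrent VTE, major bleeding and thromboembolic death. On that basis it says that "100 patients will provide more than 99% of probability observing at least 1 event, it will provide higher than 63% of probability if the event" (the second for a 1% rate). Table 7.6:1 then gives Wilson intervals for observed rates from 1% to 20%, under the caption "Expected 95% Wilson confidence interval based on 100 available patients". The section concludes that the size is adequate to pick up safety signals on the primary endpoints.

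Other sections govern how much of the 12 months will be observed:

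- Section 3.3.4.1: patients who stop drug or withdraw after Visit 2 "will be considered as “early discontinuations” and will not be replaced".
- Section 6.2.3: "Patients that are not actively taking study drug and their parent/legal guardian may be less motivated to adhere to the study visit schedule". It then lists five levels of continued participation. The lightest collects vital status only. After full withdrawal of consent, no further medical data are requested.
- Section 7.3.1, on recurrent VTE: "Patients, who do not experience recurrent VTE by the time of analyses, drop out from the study, or die from non-VTE related cause will be" treated as censored. The descriptive rate counts drop-outs as non-events.

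**The concern.** A 12-month event rate multiplied over 100 patients describes 100 patients with 12 months of observation each. Section 7.6 fixes only the number entered. It makes no allowance for patients whose later events will not be seen, while other sections expect some such patients and rule out replacing them. The sentence that carries the probabilities does not state the condition.

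These probabilities and the interval table are the only quantitative support that the protocol gives for its size. If observation is incomplete, the chance of seeing a rare VTE, major bleed or thromboembolic death is lower than printed. A report of no events could then be read as more reassuring than the follow-up supports.

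**Working it through.** **Inputs.** From Section 7.6: n = 100 (a minimum), 12-month rates p = 5% and p = 1%, and Wilson intervals at n = 100. No loss rate is given anywhere in the protocol, so the range below is an assumption.

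**Step 1: reproduce the printed probabilities.** P(at least one event) = 1 − (1 − p)^n.

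- p = 5%: 1 − 0.95^100 = 99.41%, printed as more than 99%.
- p = 1%: 1 − 0.99^100 = 63.40%, printed as higher than 63%.

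Both reproduce with n equal to 100 fully observed patients.

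**Step 2: how many complete 12-month equivalents each statement needs.**

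- More than 99% at 5%: n > ln(0.01)/ln(0.95) = 89.78, so at least 90. At 89 the probability is 98.96%.
- Higher than 63% at 1%: n > ln(0.37)/ln(0.99) = 98.93, so at least 99. At 98 it is 62.65%.

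**Step 3: probabilities over an assumed range.** Under a constant hazard, n can be read either as patients fully observed or as 100 times the mean fraction of the year observed. The formula is the same.

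| Complete 12-month equivalents | 1% rate | 5% rate |
|---|---|---|
| 100 | 63.4% | 99.4% |
| 90 | 59.5% | 99.0% |
| 80 | 55.2% | 98.3% |
| 70 | 50.5% | 97.2% |

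An equivalent is not the same as a patient retained to month 12, because a patient lost midway still contributes time. If loss accrues at a constant rate to a fraction d by 12 months, the patient-years observed are 100·d/(−ln(1 − d)). For d = 10%, 20%, 30% and 40% this is 94.9, 89.6, 84.1 and 78.3. The row for 90 therefore corresponds to roughly 20% loss spread over the year, and the row for 80 to a little under 40%.

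**Step 4: the Wilson table.** Limits = [p + z²/(2n) ± z·√(p(1 − p)/n + z²/(4n²))] / (1 + z²/n), with z = 1.96 and n = 100.

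| Observed | Computed | Printed |
|---|---|---|
| 1% | 0.18–5.45 | 0.18–5.45 |
| 2% | 0.55–7.00 | 0.55–7.00 |
| 3% | 1.03–8.45 | 1.03–8.45 |
| 4% | 1.57–9.84 | 1.57–9.89 |
| 5% | 2.15–11.18 | 2.15–11.2 |
| 10% | 5.52–17.44 | 5.52–17.4 |
| 20% | 13.34–28.88 | 13.3–28.9 |

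For the 4% row: centre (0.04 + 0.01921)/1.03842 = 0.05702; half-width 1.96 × √(0.000384 + 0.000096)/1.03842 = 0.04135; upper limit 9.84%. Every other row agrees to the precision printed.

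**The case against.** The best defence is that nothing in the two probabilities is miscalculated, that the table caption already names 100 available patients, and that 100 is a floor. Recruitment may continue, and entering 112 patients with a tenth lost leaves 112 × 0.9 = 100.8. Section 6.2.3 also asks families for the fullest follow-up that they will accept, its fourth option still collects outcome events, and sites must keep trying to locate lost patients. At the 5% planning rate the loss is small. Missing 63% by having 98 rather than 99 complete patients is partly a matter of rounding.

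Most of this stands and limits the point. It does not remove it. The caption covers the intervals, whereas the probability sentence speaks only of 100 patients. Continued recruitment is discretionary and is not tied to observed follow-up.

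A reader might infer three stronger things that the protocol does not support:

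- **That early treatment stop undermines the figures.** Section 3.1 does say that "Patients will be treated with dabigatran etexilate until the clinical risk factor requiring secondary VTE prevention has resolved, or up to a maximum of 12" (the limit is in months). However, Section 7.6 makes no claim about patient-years on drug, Section 7.3.1 does not restrict events to time on treatment, and Sections 3.1, 3.3.4.1, 6.2.3 and 7.4 plan follow-up after treatment ends. Stopping drug is not in itself planned loss of observation.
- **That the primary analysis will come before 12 months.** The current text schedules no such analysis. The idea rests on Section 7.3 being silent and on an entry in the amendment log about removed wording, and timing may be set in the statistical analysis plan.
- **That Table 7.6:1 misstates Kaplan-Meier precision.** It gives binomial intervals for an observed rate, and Section 7.3.1 also plans a descriptive rate over all treated patients. The variance method for Kaplan-Meier estimates is a matter for the statistical analysis plan.

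**Conclusion.** The point holds in a limited form. With exactly 100 patients entered, the printed probabilities are upper bounds, reached only with complete 12-month observation, and the probability sentence does not say so. The size depends on a loss rate that the protocol does not give. Across 90 to 70 complete equivalents, the probability of seeing at least one event falls by 3.9 to 12.9 percentage points at a 1% rate (63.4% to 59.5% and 50.5%). At 5% it falls by 0.4 to 2.2 points (99.4% to 99.0% and 97.2%). The consequence is therefore modest for the planning rate and material only for the rarer event. These figures assume a constant hazard and loss unrelated to risk, and recruitment beyond 100 could offset them. The 9.89 in the 4% row is a plain error of 0.05 percentage points, with no effect on any conclusion.

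**What to change.** In Section 7.6:

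1. State in the probability sentence that 99.4% and 63.4% apply to 100 patients with complete 12-month observation, and that recruitment beyond 100 may offset loss.
2. Add rows for 90, 80 and 70 complete 12-month equivalents: 59.5%, 55.2% and 50.5% at a 1% rate; 99.0%, 98.3% and 97.2% at 5%.
3. Correct the 4% row of Table 7.6:1 to 1.57–9.84.

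The cost is a change of wording and table. The stated justification becomes slightly less favourable. Enrolment, visits and data collection stay as they are.

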An open-label multicentre randomized study (the REVIVE study) comparing the efficacy and safety of a low molecular weight heparin (reviparin-sodium) to UFH/VKA for the treatment of VTE in children, showed that at 3 months post-therapy, 2/36 patients (5.6%) treated with reviparin-sodium had recurrent VTE or death compared to 4/40 patients (10.0%) receiving UFH/VKA (odds ratio = 0.53; 95% CI=(0.05, 4.00); Fisher's exact test: 2P= 0.677). There were 7 major bleeds reported, 2/36 (5.6%) in the reviparin-sodium group and 5/40 (12.5%) in UFH/VKA group (odds ratio = 0.41; 95% confidence interval 0.04, 2.76); Fisher's exact test: P=0.435). There were 5 deaths reported during the study period, 1 (2.8%) in the reviparin-sodium group and 4 (10.0%) in the UFH/VKA group. All five deaths were considered unrelated to VTE but one was due to an intracranial haemorrhage in the UFH/VKA group. Due to challenges with patient recruitment, REVIVE was closed prematurely. The REVIVE study provides valuable information on the incidence of recurrent VTE, major bleeding and problematic issues associated with therapy of VTE in children ([R06-2304](#)).

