**Proprietary confidential information.**

© 2019 Boehringer Ingelheim International GmbH or one or more of its affiliated companies. All rights reserved.

This document may not - in full or in part - be passed on, reproduced, published or otherwise used without prior written permission.

Paediatric VTE has a significant impact on both immediate and long-term health outcomes ([R13-4251](#), [P94-81556](#); [R12-5109](#)). There are two major consequences of VTE that could affect the long-term health status: recurrence of VTE and post-thrombotic syndrome (PTS). The risk of recurrent VTE in children is estimated to be approximately 5-10%. However the risk may be even higher in patients with one or more persisting risk factors (e.g. central venous line (CVL), chronic disease, thrombophilia, etc.) ([R07-2936](#); [P09-03357](#); [P12-03887](#)). Data from a recent survey conducted in the USA suggested that approximately 14% of children develop recurrent VTE with the likelihood of recurrence being the highest in adolescent group (19%) ([R13-4251](#)). The incidence of clinically significant childhood PTS is estimated to be 10% ([P09-03357](#)). Up to date, there are no randomized controlled trials that investigate secondary VTE prevention in paediatric patients.

In a prospective cohort study conducted by [redacted] and colleagues at the Hospital for Sick Children (Canada), the use of LMWH for treatment and prevention was evaluated in a cohort of 173 patients. There were 146 courses of LMWH administered for treatment and 30 courses for prophylaxis of VTE ([R14-1031](#)). Of the 30 patients who received prophylactic doses of LMWH, 11 (37%) patients received LMWH for the prevention of CVL-related thrombosis. Of these 30 patients who received prophylactic doses of LMWH, one (3.3%) patients had symptomatic recurrence of VTE, and died due to extension of old VTE and coronary heart disease. There were no major bleeds.

In another long-term safety and efficacy prospective cohort study conducted by Schobess and colleagues, 80 children aged > 3 months to < 18 years diagnosed with DVT were consecutively recruited to be treated with a LMWH and stratified to once-daily or twice-daily enoxaparin administration, with median treatment duration of 4-5 months ([R14-1032](#)). The median follow-up time was 24 months, during the follow-up period 6.3% of children developed PTS and 5% developed recurrent DVT.

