A Canadian Paediatric Registry followed 137 consecutive paediatric VTE patients from 6 months to up to 3 years ([P94-81556](#)). The registry reported that out of 137 patients, 2.2% died as a direct result of thrombotic complications, 18.5% developed recurrent VTE or PE, of which 70% occurred on anticoagulation therapy. In addition, 21% had evidence of post-thrombotic syndrome.

In summary, patients who suffered from VTE may remain at risk for recurrent thrombosis and thromboembolism after completion of initial anticoagulation treatment course, especially those with CVL, prothrombotic risk factors, etc. Long-term DVT consequences (e.g. post-thrombotic syndrome) are important causes of morbidity and mortality in children and require further investigation.

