According to the literature, the risk of bleeding tends to be in general lower in children than in adults ([R12-0738](#); [P10-09826](#)). In paediatric studies, the rate of major bleeding reported while receiving anticoagulant medication ranged from 0.5% - 1.7% of patients ([R12-0738](#)), whereas major bleeding rates in adult patients requiring oral anticoagulant therapy range from 1.3% to 8.3% per year ([P04-10723](#)). The proposed BID dosing regimen for dabigatran also appears favourable in comparison to the current standard of treatment with Vitamin K antagonists (VKAs). With VKAs, the risk of not being within the therapeutic INR range has been reported to be much higher than with this proposed dabigatran dosing regimen: published studies describe a mean or median time in therapeutic range between 39% and 81.7% ([R12-0738](#)), which means that patients are under- or overdosed for up to 60% of the time with VKA treatment.

A BID regimen with removal of capping (up to a dose of 330 mg BID) is considered favourable. In addition, risks associated with this regimen resulting from low exposure have been projected to be uncommon. Potential risks associated with higher trough exposure are transient and considered acceptable in a paediatric population in the context of less favourable treatment alternatives, specifically when comparing to the large percentage of time out of the therapeutic range with the current standard of care treatment (VKAs).

In summary, the bleeding risk in the paediatric patient population is considered to be lower than that in adult populations (e.g. in the adult SPAF and VTE indications). Based on an overall benefit-risk assessment including the fact that the risk of thrombotic events is highest

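### Section 7.6 says without limit that 100 patients can capture any safety signal, but at the 1% event rate it considers itself there is a 37% chance of seeing no event

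*Protocol*

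**What the plan says.** Section 7.6 fixes the size as a floor: "A minimum of 100 patients will be entered in this trial". It assumes a 12-month rate of 5% for a composite of recurrent VTE, major bleeding and thromboembolic death, and gives a probability above 99% of observing at least one event. For a lower rate it adds that "it will provide higher than 63% of probability if the event rate is 1" per cent. Table 7.6:1 then lists 95% Wilson intervals for observed rates from 1% to 20%. The section ends: "The sample size is considered adequate to capture any safety signal for the primary safety endpoints defined in the study".

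The primary endpoints in Section 5.2.1 are not that composite. They are recurrent VTE, bleeding (major and minor) and mortality (overall and thrombotic). Section 7.3.1 gives each its own Kaplan-Meier summary; for example, "overall mortality and mortality related to thromboembolic events will be analysed as time-to-event".

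The protocol also cites background rates for some components:
- Major bleeding, Section 2.3: "the rate of major bleeding reported while receiving anticoagulant medication ranged from 0.5% - 1.7% of patients", with no time base.
- Major bleeding, Section 1.1, from a randomised trial of acute treatment: "There were 7 major bleeds reported, 2/36 (5.6%) in the reviparin-sodium group and 5/40 (12.5%) in UFH/VKA group".
- Thrombotic death, Section 1.1, from a registry with 6 months to 3 years of follow-up: "out of 137 patients, 2.2% died as a direct result of thrombotic complications".
- Recurrence, Section 1.1: "The risk of recurrent VTE in children is estimated to be approximately 5-10" per cent.

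**The concern.** The closing sentence covers every primary endpoint at every rate. The figure above 99% belongs to a composite at 5%, the most favourable case for the components inside it. The figure of 63% at 1%, given in the same paragraph, shows that a rare event would often not appear at all.

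What is at stake is how a zero is read. If no major bleed or no thrombotic death is seen, the sentence invites the conclusion that there is no signal. One hundred patients cannot show that.

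**Working it through.** **Inputs.** n = 100, and rates of 5% and 1%, from Section 7.6. Component rates come from Sections 1.1 and 2.3. All 100 patients are taken as followed for 12 months. The 0.5%–1.7% and 2.2% figures are treated as 12-month risks. That is an assumption, because the first has no time base and the second covers 6 months to 3 years. The acute-trial bleeding rates and the recurrence range are used in the same way.

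**1. The protocol's own figures.** P(at least one event) = 1 − (1 − p)^100.
- p = 5%: 1 − 0.95^100 = 99.4% (stated: above 99%).
- p = 1%: 1 − 0.99^100 = 63.4% (stated: above 63%).

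Both reproduce. The complement at 1% is 0.99^100 = 36.6%. The protocol states the 1% case for the composite, but the formula uses only n and p, so it holds equally for a single component at 1%.

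**2. The rates cited in the protocol.**

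| Source | Rate | P(at least one in 100) |
|---|---|---|
| Major bleeding, Section 2.3, low end | 0.5% | 39.4% |
| Major bleeding, Section 2.3, high end | 1.7% | 82.0% |
| Thrombotic death, registry, Section 1.1 | 2.2% | 89.2% |
| Recurrent VTE, Section 1.1, low end | 5% | 99.4% |
| Major bleeding, acute trial, Section 1.1 | 5.6% | 99.7% |
| Major bleeding, acute trial, Section 1.1 | 12.5% | above 99.9% |

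**3. The limit that 100 patients support.** The risk needed for detection probability q is p = 1 − (1 − q)^(1/100).
- q = 80%: 1.60%
- q = 90%: 2.28%
- q = 95%: 2.95%
- q = 99%: 4.50%

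The protocol does not say which q it requires. For scale, a 95% chance of at least one event at a 1% rate would need ln(0.05)/ln(0.99), rounded up to 299 patients.

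**4. What zero events would show.** For 0/100 the two-sided 95% Wilson upper limit is z²/(n + z²) = 3.8415/103.8415 = 3.70%.

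**5. Table 7.6:1, 4% row.** With z = 1.96 (z² = 3.8415):
- Centre = (0.04 + 3.8415/200)/(1 + 0.038415) = 0.05702.
- Half-width = 1.96 × √(0.04 × 0.96/100 + 3.8415/40000)/1.038415 = 0.04135.
- Interval = 1.57% to 9.84%.

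The table prints 9.89. The other six rows reproduce at the printed precision. A continuity-corrected Wilson limit would be 10.51 and a Clopper-Pearson limit 9.93, so neither accounts for 9.89.

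**The case against.** The best defence is that nothing is hidden. The 63% stands two sentences before the conclusion, and the table gives an upper limit of 5.45% at an observed 1%. On this view the fault is one loose word in a closing judgement. That is fair as to motive and size, but printing 63% beside a claim about *any* signal contradicts the claim and does not limit it.

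A second argument is that a signal means an excess over background, not one event. A risk tripled from 1% to 3% would produce at least one event with 95.2% probability. But one event does not reveal the excess, because at the unchanged 1% it would occur 63.4% of the time. Reading a signal as an excess sets a stricter test, which 100 patients are less likely to meet.

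A third argument is that no component has been shown to be so rare. This stands in part. The low bleeding range has no time base, the acute trial reports far higher rates, recurrent VTE at the cited 5–10% is well covered, and overall mortality and minor bleeding are not examined here. The finding does not depend on settling this, because the protocol's own 1% scenario is enough to defeat an unlimited claim.

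It is also true that nothing formal hangs on the sentence. There is no hypothesis test (Section 7.2), the size was agreed with the Paediatric Committee, recruitment may continue beyond 100, and the data monitoring committee follows the whole programme (Section 3.1.1.1). These points limit the consequence, but they do not make the sentence true.

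**Conclusion.** The concern holds, and it is minor. The probabilities in Section 7.6 are right; the conclusion drawn from them is too wide. At a true 12-month risk of 1% the trial has a 36.6% chance of showing no event. The chance of showing at least one reaches 95% only from a risk of about 3%. This rests on 100 patients fully followed to 12 months; early loss would generally lower the detection probabilities.

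That 1% is missed in more than a third of such trials is certain. Which primary components are that rare is not: applying the cited rates for major bleeding and thrombotic death requires reading them as 12-month risks. The finding does not say that the trial is too small for its descriptive purpose.

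The table error is separate and small, 0.05 percentage points in one limit.

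**What to change.** Replace the last sentence of Section 7.6 with:

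> If all 100 patients are followed for 12 months, the probability of observing at least one event is 95% or more for endpoints with a true 12-month risk of about 3% or more (80% at 1.6%, 99% at 4.5%) and is lower for rarer events. Separately, if no event is observed, the two-sided 95% Wilson upper limit is 3.7%.

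Leading with 95% is a choice, since the protocol sets no required probability; the 80% and 99% points let the reader apply another. In Table 7.6:1, change the upper limit in the 4% row from 9.89 to 9.84.

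The cost is one sentence and one table entry. The stated claim becomes less favourable.
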